6.4.3.2 AEs and SAEs

AEs will be summarized using MedDRA System Organ Class and preferred terms. Tables will show by treatment arm the number and percentage of participants experiencing an AE within a System Organ Class or within preferred term category by severity or by relationship to study product. For the calculations in these tables, a participant with multiple AEs within a category will be counted once under the maximum severity or the strongest recorded causal relationship to study product. Formal statistical testing comparing arms is not planned since interpretation of differences must rely heavily upon clinical judgment.

A listing of SAEs reported to the DAIDS Regulatory Support Center (RSC) Safety Office will provide details of the events including severity, relationship to study product, time between onset and last infusion, and number of infusions received.

6.4.3.3 Local laboratory values

Boxplots of local laboratory values will be generated for baseline values and for values measured during the course of the study by treatment arm and visit. Each boxplot will show the first quartile, the median, and the third quartile. Outliers (values outside the boxplot) will also be plotted. If appropriate, horizontal lines representing boundaries for abnormal values will be plotted.

For each local laboratory measure, summary statistics will be presented by treatment arm and timepoint, as well as changes from baseline for postenrollment values. In addition, the number (percentage) of participants with local laboratory values recorded as meeting Grade 1 AE criteria or above as specified in the DAIDS AE Grading Table (see Section 11.2) will be tabulated by treatment arm for each postinfusion timepoint. Reportable clinical laboratory abnormalities without an associated clinical diagnosis will be included in the tabulation of AEs described above.

6.4.3.4 Reasons for discontinuation of study product administration and early study termination

The number and percentage of participants who discontinue study product administration and who terminate the study early will be tabulated by reason and treatment arm.

6.4.4 Analysis of drug-level endpoints

6.4.4.1 General approach

For the statistical analysis of endpoints, data from enrolled participants will be used according to the initial randomization assignment regardless of how many infusions they received. Additional analyses may be performed, limited to participants who received all scheduled infusions per protocol. Assay results that are unreliable, from specimens collected outside of the visit window, or from HIV-infected participants postinfection will be excluded. Since the exact date of HIV infection is unknown, any assay data from blood draws 4 weeks prior to an infected participant's last seronegative sample and thereafter may be excluded. If an HIV-infected participant does not have a seronegative sample postenrollment, then all data from that participant may be excluded from the analysis.

For continuous assay data (eg, serum concentration of VRC01), graphical and tabular summaries of the distributions by treatment arm and timepoint will be made. Scatterplot matrix with correlation coefficient information between each pair of serum and mucosa drug levels at different timepoints will be provided. An appropriate data transformation (eg, log transformation) may be applied prior to testing to better satisfy analysis assumptions. Inference from these analyses would be limited by the small sample sizes of the groups.

For qualitative assay variables (eg, positive or negative), the analyses will be performed by tabulating the frequency of positive responses for each assay by group at each timepoint at which an assessment is performed. Crude response rates will be presented with their corresponding 95% confidence interval estimates calculated using the score test method (64).

More sophisticated analyses of drug-level data and other assay data collected over time employing repeated measures methodology that is valid under the missing at random (MAR) assumption (for example, nonlinear mixed effects models) may

be utilized to incorporate outcome responses over several timepoints and to account for subject heterogeneity. MAR assumes that the probability of an observation being missing may depend upon the observed responses and upon observed covariates, but not upon any unobserved factors. Generalized nonlinear models for response rates will use a binomial error distribution and for quantitative endpoints, a normal error distribution. All models will include as covariates all available baseline predictors of the missing outcomes.

In addition, non-compartment PK analysis will be performed to estimate PK parameters from individual time-concentration curves. The correlation between individual-level PK parameters estimated for different specimen types (serum vs. mucosa) may also be assessed. All statistical tests will be 2-sided and will be considered statistically significant if $p \leq 0.05$.

For the analysis of correlation between two continuous assay variables over time, graphical summary and tabular summary of the sample correlation at each given timepoint will be made. Cross-correlation of the 2 variables with different time lags may also be calculated and visually displayed if there are at least 10 participants with no missing data over time from both variables. Nonlinear or linear mixed effects models may also be used to predict mucosal drug levels based on serum drug levels collected at the same or previous timepoints. More details of the statistical analysis approaches will be described in a separate Statistical Analysis Plan document.

6.4.5 Analyses prior to end of scheduled follow-up visits

Any analyses conducted prior to the end of the scheduled follow-up visits should not compromise the integrity of the trial in terms of participant retention or safety, drug level or functional endpoint assessments.

6.4.5.1 Safety

During the course of the trial, analyses of safety data will be prepared approximately every 4 months, as defined in Section 3, for review by the SMB. Ad hoc safety reports may also be prepared for SMB review at the request of the PSRT. The HVTN leadership must approve any other requests for safety data prior to the end of the scheduled follow-up visits.

6.4.5.2 Anti-VRC01, anti-VRC01LS and other Laboratory Assessments

Generally, analysis of a primary laboratory endpoint may be performed when all participants have completed the corresponding visit and data are available for analysis from at least 80% of these participants. The Laboratory Program will review the analysis report prior to distribution to the protocol chairs, DAIDS, vaccine developer, and other key HVTN members and investigators. Distribution of reports will be limited to those with a need to know for the purpose of informing future trial-related decisions.

7 Selection and withdrawal of participants

Participants will be healthy, HIV-uninfected (seronegative) adults who comprehend the purpose of the study and have provided written informed consent. Volunteers will be recruited and screened; those determined to be eligible, based on the inclusion and exclusion criteria, will be enrolled in the study. Final eligibility determination will depend on results of laboratory tests, medical history, physical examinations, and answers to self-administered and/or interview questions.

Investigators should always use good clinical judgment in considering a volunteer's overall fitness for trial participation. Some volunteers may not be appropriate for enrollment even if they meet all inclusion/exclusion criteria. Medical, psychiatric, occupational, or other conditions may make evaluation of safety and/or pharmacokinetics difficult, and some volunteers may be poor candidates for retention.

Determination of eligibility, taking into account all inclusion and exclusion criteria, must be made within 56 days prior to enrollment unless otherwise noted in Sections [7.1](#) and [7.2](#).

7.1 Inclusion criteria

General and Demographic Criteria

1. **Age** of 18 to 50 years
2. **Weight** \leq 115 kg
3. **Access to a participating HVTN CRS** and willingness to be followed for the planned duration of the study
4. Ability and willingness to provide **informed consent**
5. **Assessment of understanding**: volunteer demonstrates understanding of this study; completes a questionnaire prior to enrollment with verbal demonstration of understanding of all questionnaire items answered incorrectly
6. **Agrees not to enroll in another study** of an investigational research agent until completion of the last study visit
7. **Good general health** as shown by medical history, physical exam, and screening laboratory tests

HIV-Related Criteria:

8. Willingness to receive **HIV test results**

9. Willingness to discuss HIV infection risks and amenable to HIV risk reduction counseling.
10. Assessed by the clinic staff as being at “**low risk**” for **HIV infection** [low risk guidelines are found on the protocol home page on the HVTN Members’ site (<https://members.hvtn.org/protocols/hvtn116>)] and committed to maintaining behavior consistent with low risk of HIV exposure through the last required protocol clinic visit.

Laboratory Inclusion Values

Hemogram/CBC

11. **Hemoglobin** \geq 11.0 g/dL for volunteers who were born female, \geq 13.0 g/dL for volunteers who were born male
12. **White blood cell count** = 2,500 to 12,000 cells/mm³
13. **Total lymphocyte count** \geq 800 cells/mm³
14. **Remaining differential** either within institutional normal range or with site physician approval
15. **Platelets** = 125,000 to 550,000/mm³

Chemistry

16. **Chemistry panel:** ALT, AST, and alkaline phosphatase $<$ 1.25 times the institutional upper limit of normal; creatinine \leq institutional upper limit of normal.

Virology

17. **Negative HIV-1 and -2 blood test:** US volunteers must have a negative FDA-approved enzyme immunoassay (EIA). Non-US sites may use locally available assays that have been approved by HVTN Laboratory Operations.
18. **Negative Hepatitis B surface antigen (HBsAg)**
19. **Negative anti-Hepatitis C virus antibodies (anti-HCV),** or negative HCV polymerase chain reaction (PCR) if the anti-HCV is positive

Urine

20. **Normal urine:**
 - Negative urine glucose, and
 - Negative or trace urine protein, and

- Negative or trace urine hemoglobin (if trace hemoglobin is present on dipstick, a microscopic urinalysis with red blood cells levels within institutional normal range).

Reproductive Status

21. **Volunteers who were born female:** negative serum or urine beta human chorionic gonadotropin (β -HCG) pregnancy test performed prior to initial biopsy for groups 1-3 and prior to initial infusion for groups 4-5 on the day of enrollment. Persons who are NOT of reproductive potential due to having undergone bilateral oophorectomy (verified by medical records), are not required to undergo pregnancy testing.

22. **Reproductive status:**

United States

A volunteer who was born female must:

- Agree to consistently use effective contraception (see [Appendix C](#)) for sexual activity that could lead to pregnancy from at least 21 days prior to enrollment through the last required protocol clinic visit. Effective contraception is defined as using the following methods:
 - Condoms (male or female) with or without a spermicide,
 - Diaphragm or cervical cap with spermicide,
 - Intrauterine device (IUD),
 - Hormonal contraception, or
 - Any other contraceptive method approved by the HVTN 116 PSRT
 - Successful vasectomy in the male partner (considered successful if a volunteer reports that a male partner has [1] documentation of azoospermia by microscopy, or [2] a vasectomy more than 2 years ago with no resultant pregnancy despite sexual activity postvasectomy);
- Or not be of reproductive potential, such as having had a bilateral oophorectomy, or tubal ligation;
- Or be sexually abstinent.

South Africa

A volunteer who was born female must:

- Agree to consistently use effective contraception (see [Appendix D](#)) for sexual activity that could lead to pregnancy from at least 21 days prior to enrollment

through the last required protocol clinic visit. Effective contraception for participants in South Africa is defined as using 2 methods of birth control.

ONE barrier contraceptive method:

- Condoms (male or female)
- Diaphragm or cervical cap

PLUS ONE of the following methods:

- Intrauterine device (IUD),
 - Hormonal contraception, or
 - Successful vasectomy in the male partner (considered successful if a volunteer reports that a male partner has [1] documentation of azoospermia by microscopy, or [2] a vasectomy more than 2 years ago with no resultant pregnancy despite sexual activity postvasectomy), or
 - Any other contraceptive method approved by the HVTN 116 PSRT
- Or not be of reproductive potential, such as having had a bilateral oophorectomy, or tubal ligation;
 - Or be sexually abstinent.

23. **Volunteers who were born female must also agree not to seek pregnancy through alternative methods**, such as artificial insemination or *in vitro* fertilization until after the last required protocol clinic visit

Mucosal Specimen Collection

24. **Volunteers 21 years of age and older who were born female:** Pap smear (verified by medical records) is required within:

- the 3 years prior to enrollment with the latest result reported as normal or ASCUS (atypical squamous cells of undetermined significance), OR
- the 5 years prior to enrollment, with the latest result reported as normal, or ASCUS with no evidence of high risk HPV.

If no Pap smear was done within the last 3 years (or within the last 5 years, if high risk HPV testing was performed), the volunteer must be willing to undergo a Pap smear with the result reported (verified by medical records) as normal or ASCUS prior to sample collection.

25. **Willing to have mucosal secretions and tissue biopsies collected**

26. **Willing to abstain from sexual intercourse for the required period after each biopsy collection**

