5.1 Primary objectives and endpoints

Primary objective 1

- To evaluate the safety and tolerability of VRC01/VRC01LS mAb administered through IV infusion

Primary endpoint 1

- Local and systemic reactogenicity, laboratory measures of safety, AEs, SAEs, and rates of discontinuation

Primary objective 2

- For each sex at birth, to evaluate the pharmacokinetics of VRC01 in serum versus mucosa in each mucosal compartment

Primary endpoints 2 (Groups 1 & 2 & 4)

- Serum concentration of VRC01 out to Month 6 after the last infusion
- Levels of VRC01 in genital and rectal secretions, as well as cervical, vaginal, and rectal tissues at the collection timepoints

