9.3 Enrollment visits

Enrollment in Groups 1, 2, and 3 is simultaneous with baseline biopsy collections on day -14. Enrollment in Groups 4 and 5 is simultaneous with the infusion on day 0. The time interval between randomization and first infusion should not exceed 4 working days. The CRS requests the randomization assignment from the Web-based randomization system. Randomization will be performed prior to first infusion for all groups.

At the baseline biopsy collection visit (Groups 1-3; day -14), cervical, vaginal, and/or rectal biopsies will be collected. These samples will serve as baseline controls and will help to assess the acceptability of the biopsy procedures to participants and the fitness of participants to continue in these groups with extensive mucosal biopsy collections. Participants with conditions not amenable to repeated biopsy sampling or participants not willing to continue in the trial after these baseline biopsies have been performed may be replaced.

At the baseline biopsy collection visit (Groups 1-3; day -14), the following procedures are performed:

- Abbreviated physical examination, including weight, vital signs, and a symptom-directed evaluation by history and/or appropriate physical exam based on participant self-reported symptoms or complaints
- Assessment of concomitant medications (Section 9.2)
- Assessment of any new or unresolved AEs/intercurrent illnesses
- Urine or serum pregnancy test (for participants who were born female). Persons who are NOT of reproductive potential due to having undergone bilateral oophorectomy (verified by medical records), are not required to undergo pregnancy testing
- Risk reduction counseling (Section 9.7)
- Pregnancy prevention assessment (Section 9.2 and 9.8)

- Assessment of new or unresolved social impacts (site staff will ask participant about the status of any unresolved social impacts and if s/he has experienced any new social impacts as a result of the trial participation)
- Specimen collection (including mucosal sampling as described in Section 9.6);
- HSV 1/2 testing
- Blood hormone levels (estradiol and progesterone) (persons born female only)
- Confirm that participants received HIV test results from previous visit. If not, provide test results and post-test counseling as appropriate.

For the enrollment infusion visit (Groups 4 and 5; day 0) procedures are described in Section 9.4.

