 - Biopsies will be collected a minimum of 28 days from previous biopsies.
 - Participants should not have taken antithrombotic medication (except ASA and NSAIDs) for 5 days prior to the procedure. If a participant is taking these medications for medical reasons, biopsies should not be collected and these medications should not be interrupted.
 - Participants should not have rectal sex and/or insert any foreign object or substance into the rectum for **5 days after** biopsy samples have been collected;
 - Participants should contact the clinic if they experience a large amount of bleeding, have a temperature of more than 38.1°C (100.5°F), experience chills, or have pain that is not improving.
- Cervicovaginal secretion and/or biopsy sampling. Participants who are age 21 or older must report having had a Pap smear within the 5 years prior to enrollment, with the latest result reported as normal, or ASCUS (atypical squamous cells of undetermined significance) with no evidence of high-risk HPV; if high-risk HPV testing was not conducted, the participant must report having had a Pap smear within the 3 years prior to enrollment, with the latest result reported as normal or ASCUS. Pap smear results must be verified by medical records. For participants capable of becoming pregnant, a pregnancy test must be performed and must be negative prior to any cervicovaginal mucosal sampling with a sponge. For sampling with menstrual cup, the pregnancy test can be performed after collection has taken place, but should be performed on the same day as the collection. Cervicovaginal mucosal sampling should be deferred if a participant is menstruating, but should be performed as soon as possible, within the visit window. If this is not possible, cervicovaginal biopsies may be collected within the visit window during menses at the clinician's discretion. In addition, cervicovaginal sampling will not be performed (or may be deferred to a later date within the visit window) if a participant has an active ulcerative genital lesion or is known to have an active GTI at the scheduled timepoint. Participants providing cervicovaginal samples should be advised as follows:
 - Do not use anything with spermicide, lubricants, or topical/intravaginal medications (eg, topical yeast infection treatments) for 48 hours before the samples are collected;
 - Do not douche for 48 hours before the samples are collected;

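### Criterion 24 and Section 9.6 disagree on ASCUS with high-risk HPV detected: such a woman aged 21 or older may enroll but fails the condition for cervicovaginal sampling

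*Protocol*

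**What the plan says.** Criterion 24 (Protocol Section 7.1) applies to volunteers born female and aged 21 or older. It gives two routes joined by OR:

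- first bullet, a Pap dated in "the 3 years prior to enrollment with the latest result reported as normal or ASCUS";
- second bullet, a Pap dated in "the 5 years prior to enrollment, with the latest result reported as normal, or ASCUS with no evidence of high risk HPV".

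A closing paragraph begins "If no Pap smear was done within the last 3 years (or within the last 5 years, if high risk HPV testing was performed" and then requires a new Pap smear, whose result need only be normal or ASCUS.

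Section 9.6 sets the condition for cervicovaginal secretion and biopsy sampling at the same ages. There, a woman "must report having had a Pap smear within the 5 years prior to enrollment, with the latest result reported as normal, or ASCUS". That ASCUS result counts only when nothing in the record points to high-risk HPV. One exception is given: "if high-risk HPV testing was not conducted, the participant must report having had a Pap smear within the 3 years prior to enrollment". Under this exception the accepted results are again normal or ASCUS.

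Section 9.2, on pre-enrollment procedures, sends the screener to criterion 24 alone for the Pap requirement. The Pap footnote in Appendices L to O cites Sections 7.1 and 9.6 together.

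Primary endpoint 2 (Section 5.1; Groups 1, 2 and 4) includes "Levels of VRC01 in genital and rectal secretions, as well as cervical, vaginal, and rectal tissues at the collection timepoints".

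**The concern.** A single set of women should be both eligible and sampleable, because cervicovaginal material is what women at most sites contribute to the mucosal part of primary endpoint 2. If the two rules differ, one of two things can happen to a woman in the gap. Staff following criterion 24 enroll her and staff following Section 9.6 then decline to sample her, so she gives serum but no cervicovaginal data. Or she is sampled, biopsies included, although Section 9.6 excludes her. The first loses endpoint data, and the second is an invasive procedure outside one of the protocol's own conditions.

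**Working it through.** **Step 1: apply both rules to every case.** Take Pap age (up to 3 years, 3 to 5 years, over 5 years), result (normal, ASCUS) and high-risk HPV status (not tested, negative, positive): 3 x 2 x 3 = 18 combinations. Two reading assumptions apply to both texts: the HPV condition attaches to ASCUS and not to a normal result, and an untested ASCUS does not count as having no evidence of HPV. The criterion 24 column uses its two bullets as written. Neither rule accepts a Pap over 5 years old, which leaves these rows:

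| Pap age | Result | HPV | Criterion 24 bullets | Section 9.6 |
|---|---|---|---|---|
| up to 3 y | normal | any | yes | yes |
| up to 3 y | ASCUS | not tested or negative | yes | yes |
| up to 3 y | ASCUS | positive | **yes** | **no** |
| 3 to 5 y | normal | negative or positive | yes | yes |
| 3 to 5 y | normal | not tested | **yes** | **no** |
| 3 to 5 y | ASCUS | negative | yes | yes |
| 3 to 5 y | ASCUS | not tested or positive | no | no |

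Two of the 18 combinations disagree, both as eligible but not sampleable. None disagrees the other way.

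**Step 2: grade the two.** The first (ASCUS, HPV positive, within 3 years) is a direct conflict. It also arises when the new Pap required by the closing paragraph returns ASCUS with HPV detected, since that paragraph sets no HPV condition. The second (normal, 3 to 5 years old, untested) is a wording ambiguity. The second bullet read alone accepts it, but criterion 24's closing paragraph calls for a new Pap, as Section 9.6 does.

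**Step 3: when the mismatch would surface.** The Section 9.6 condition covers secretions as well as biopsies. In Groups 1-3 it first applies at the day -14 sampling, before any infusion, and Section 9.3 allows replacement of participants whose condition is not amenable to repeated biopsies. In Groups 4 and 5, "Enrollment in Groups 4 and 5 is simultaneous with the infusion on day 0" and biopsies start afterwards, but secretions are collected as part of screening, up to the infusion (Section 9.2; Appendices J and K, note 18). So the check falls before infusion in every group, although no passage says to withhold infusion if it fails.

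**Step 4: size.** Inputs from Section 6.1.2: 13 women in each of Groups 1 and 2 and 8 in Group 4, 15% missing data, and Z' = arctanh(rho) + rho/(2(n-1)) with a normal approximation. The test is two-sided at 0.05 (Section 6.4.4.1).

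First, the protocol's own figure. Groups 2+4 have 13 + 8 = 21 women; 0.85 x 21 = 17.85, rounded down to 17. At rho 0.7, Z' = 0.867 + 0.7/32 = 0.889; multiplied by sqrt(14) = 3.742 this is 3.33, and 3.33 - 1.96 = 1.37, which is about 91%. With a t-based critical value it is 91.3%. Table 6-3 gives 91; all 49 of its cells reproduce within 0.5 points by the t-based version.

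Next, suppose k women cannot be sampled. The documents give no prevalence, so k is an assumption, with all k taken from the pool shown:

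| k | Groups 2+4: n | power, rho 0.7 | Groups 1+2+4: n | power, rho 0.6 |
|---|---|---|---|---|
| 0 | 17 | 91.3% | 28 | 94.0% |
| 1 | 17 | 91.3% | 28 | 94.0% |
| 2 | 16 | 89.3% | 27 | 93.2% |
| 4 | 14 | 84.1% | 25 | 91.1% |
| 6 | 12 | 76.7% | 23 | 88.4% |

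For k = 1: 0.85 x 20 = 17.0 and 0.85 x 33 = 28.05, so neither n changes. (The 28 is Table 6-3's column, from 0.85 x 34 = 28.9; the Section 6.1.2 text says 25 women.)

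**The case against.** The strongest answer is that the protocol already stops such a woman before it matters. The Pap smear is a screening procedure and its appendix footnote cites both sections, so a careful site would apply the narrower of the two at screening. Section 7 says some volunteers may be unsuitable even if they meet every criterion, and exclusion 29 lets the clinician exclude for anything in the medical history that contraindicates mucosal sampling. The sampling criteria are also said to be in the Study Specific Procedures, which are not available here and may settle the point.

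This makes harm less likely but does not remove the conflict. Section 9.2 names criterion 24 only. The discretionary clauses state no Pap or HPV condition, so two sites can use them differently.

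The objection does dispose of three stronger readings that a reader might infer:

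- *That women will be infused with no chance of catching the problem, above all in Groups 4 and 5.* Screening secretions there, and the day -14 sampling in Groups 1-3, bring the Section 9.6 check forward to before infusion.
- *That a normal Pap 3 to 5 years old without HPV testing is a second full conflict.* Criterion 24's closing paragraph largely answers it.
- *That power suffers materially.* In Group 4 alone at rho 0.9, the formula falls from 77% (n=6) to 62% (n=5) for one lost woman, but that comes from rounding 6.8 and 5.95 down to 6 and 5 in the smallest arm. Section 6.1.2 calls power limited at n=6 or lower and rests the drug-level objective on the combined VRC01 groups.

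Nor would an affected woman be lost to primary endpoint 2 entirely. She still gives serum and, at the Seattle site if she agrees, rectal samples.

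**Conclusion.** The two passages conflict for one defined group: women aged 21 or older with ASCUS and high-risk HPV detected, on a Pap within 3 years or on the new screening Pap. They meet criterion 24 and fail Section 9.6. A lesser ambiguity lies inside criterion 24, between its second bullet and its closing paragraph.

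The number affected is unknown and probably small. The conflict needs an HPV result to exist, and the test list in Section 9.2 does not include one. One affected woman would leave the pooled n at 17 and 28, and two would cost 2.0 points (Groups 2+4) or 0.8 points (Groups 1+2+4). The case for change is therefore not power. It is that two rules on enrollment and on an invasive procedure give different answers for the same woman. The conclusion rests on the reading assumptions in the working. If the HPV condition were taken to cover normal results too, a normal, HPV-positive Pap within 3 years would also fall in the gap.

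**What to change.** Reconcile the passages. State one Pap/HPV condition in criterion 24, with the two bullets and the closing paragraph (including the required result of a new Pap) consistent with one another. Have Section 9.6 refer to criterion 24 and not restate it. The pointers in Section 9.2 and Appendices L to O then lead to the same rule, and the same women qualify for enrollment and for cervicovaginal sampling. Which condition applies is for the protocol's clinicians to decide.

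The cost is a clarification memo or letter of amendment; Section 9.6 was already clarified by memo in June 2016. At most a few women would be screened differently, and no analysis or sample size changes.
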